3.4 DIETARY INTAKE

A stable dietary intake should be maintained including high fiber diet, fiber supplements, vitamins and minerals, probiotics, fish oil, during the study. Patients must have been on a stable dietary regimen for at least 30 days before Visit 1, and are expected to remain on that diet, including all supplements, for the duration of the study.

4 VARIABLES AND METHODS OF ASSESSMENT

4.1 DEMOGRAPHICS AND BASELINE CHARACTERISTICS

4.1.1 Patient Demography

Patient demography consists of:

- Age at screening (date of birth)
- Race
- Ethnicity
- Sex (Gender)
- Height (m), without shoes
- Weight (kg) and BMI

BMI will be calculated by measuring the patient's height (without patient wearing shoes) and weight and using these measurements (in meters and kilograms) in the formula: $BMI \text{ (kg/m}^2\text{)} = \text{weight (kg)} \div \text{height}^2 \text{ (m}^2\text{)}$

4.1.2 Disease and Medical History

A complete medical history, including history of GI diseases, should be recorded for all patients. Source documentation for diagnoses, previous treatments and interventions, where available, should be included in the patient's medical record to facilitate source documentation verification. Confirmation of diagnosis of CIC is required as part of evaluation for this study; if not previously documented in the patient's medical history, the diagnosis must be included in the patient's medical record for the purpose of source document verification.

4.1.3 Previous Medications and Diet

At the Screening Visit (Visit 1), the clinical site will ensure the patient is not or has not been on prohibited medications, supplements or investigational agents during the specified time (see **Section 3.3.2**). If the patient has used a prohibited medication within the proscribed time period prior to Visit 1, the site needs to assure that the required washout period for the medication is completed before commencement of the 2-week baseline diary assessments. Previous medications will be documented as described in **Section 3.3**.

The diet history of each patient will be reviewed at Screening (Visit 1) to determine if the patient has been on a stable diet for the last 30 days, and whether the patient agrees to remain on that diet for the duration of the study.

4.2 EFFICACY VARIABLES

4.2.1 Data Collected via the Electronic Diary

At the Screening Visit (Visit 1), patients will be instructed on the use of the electronic diary and the importance of daily diary reports. Episodic or "real time" calls should be made at the time of each bowel movement or use of rescue medication during the course of the day. End of Day calls should be made only once per day (between 7 pm to 11:59 pm each day). **Patients will begin using the electronic diary following training at Visit 1 and will continue using it through the Posttreatment Period.**

The electronic diary will be activated at the Screening Visit (Visit 1) in order for the patient to become familiar with its daily use to record their BMs, rescue medication intake and constipation symptoms. Note that any data entered prior to the beginning of the 2-week baseline diary assessment will be utilized for assessment of compliance only and will not be saved.

The electronic diary is designed for:

- **Episodic reporting** of each bowel movement (BM) and rescue medication (RM) use in “real-time” as they occur throughout a 24-hour period (Patients may report BMs and RM use as often as necessary);
- **End-of-Day daily reporting** constipation-related symptoms (and BM/RM if not already reported as an ‘episodic report’) at a specific time each evening. Patients who have not completed the prompted evening call will receive an automated reminder (via phone) each evening.

To remain eligible for the study, patients must complete at least 5 of the 7 days of electronic End-of-Day diary entries for each of the 2 weeks of Baseline diary period.

Compliance with diary entries should be a focus for patient education at all study visits.

The following endpoints will be assessed using data collected via the electronic diary:

Frequency and Completeness of Bowel Movements

Patients will be asked to report in “real time” the numbers of BMs they experienced each day, the time of each BM, and the completeness of evacuation in the daily BM Diary. Frequency of BMs is one aspect of the primary endpoint for evaluation of study drug efficacy.

Stool Consistency—Bristol Stool Form Scale (BSFS)

Patients will be asked to rate their stool consistency according to the BSFS (see **Appendix C**), which will be provided to them in the form of a laminated card (and will appear on the appropriate electronic hand-held device screen) at the Screening Visit (Visit 1), and may be referred to as often as necessary throughout the Screening, Treatment and Posttreatment Periods. The BSFS is a validated measure of stool consistency commonly used in clinical trials.

Use of Rescue Medication (RM)

As part of the daily diary, the patient will be questioned concerning the use of provided rescue medication (Dulcolax®), including time of use, frequency of use, and amount of rescue medication used. Use of rescue medication will determine whether a BM was spontaneous, but only this aspect of rescue medication use is part of the primary endpoint.

Constipation-related Symptoms

The patient will also record in the electronic diary the frequency and severity of several CIC-related gastrointestinal symptoms. These symptoms include abdominal pain, abdominal bloating, abdominal discomfort, straining during bowel movement and pain with defecation. Patients will be asked to rate their symptoms on an 11-point Numeric Rating Scale from 0 (NO) to 10 (WORST POSSIBLE) (See **Appendix D**).

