cGMP	Cyclic guanosine monophosphate
CMH	Cochran-Mantel-Haenszel (test)
CRO	Contract Research Organization
CSBM	Complete spontaneous bowel movement
CTCAE	Common Terminology Criteria for Adverse Events
DRE	Digital rectal examination
ECG	Electrocardiogram
eCRF	Electronic Case Report Form
EDC	Electronic data capture
EOS	End of Study
EOT	End of treatment
FDA	Food and Drug Administration
FSH	Follicle Stimulating Hormone
GC-C	Guanylate cyclase C
GCP	Good Clinical Practice
GI	Gastrointestinal
IBS	Irritable Bowel Syndrome
ICF	Informed consent form
ICH	International Conference on Harmonization
IND	Investigational New Drug (application)
IRB	Institutional Review Board
ITT	Intent-to-Treat
IWRS	Interactive Web-based Response System
LAR	Legally authorized representative
LLN	Lower limit of normal
LOCF	Last observation carried forward
LS	Least Squares
MCG	Microgram
MCH	Mean corpuscular hemoglobin
MCV	Mean corpuscular volume
MedDRA	Medical Dictionary for Regulatory Activities
MG	Milligram
MITT	Modified Intent-to-Treat
mL	Milliliter
PDUFA	Prescription Drug User Fee Act

PE	Physical examination
PGA	Patient Global Assessment
PI	Principal Investigator
PIN	Personal Identification Number
PP	Per-Protocol (Population)
PRO	Patient Recorded Outcome
PV	Pharmacovigilance
QD	Once daily
QoL	Quality of Life
RM	Rescue medication
RTSM	Randomization and Trial Supply Management
SAE	Serious adverse event
SAP	Statistical analysis plan
SBM	Spontaneous bowel movement
SD	Standard deviation
SOC	System organ class
SP-304	Previous designation for Plecanatide
TEAE	Treatment emergent adverse event
TSH	Thyroid stimulating hormone
ULN	Upper limit of normal
US	United States
WHODD	World Health Organization Drug Dictionary

Definition of Terms

[figure not shown]
Spontaneous bowel movement (SBM)	A bowel movement that occurs in the absence of laxative use within the preceding 24 hours
Complete spontaneous bowel movement (CSBM)	A spontaneous bowel movement with the sense of complete evacuation

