9. The patient has clinical or laboratory signs and symptoms of significant cerebral, respiratory, renal, hepatobiliary, pancreatic, intestinal (including acute appendicitis, inflammatory bowel disease, or undiagnosed abdominal pain), endocrinologic, or infectious disease that in the investigator's judgment could interfere with study assessments or completion of the study. (Note: A patient with a history of thyroid disease may be enrolled if he or she has normal T3 and T4 at Screening. If the patient is taking medication for active thyroid disease, his or her T3 and T4 level must be within normal limits and the dose of any medication used to treat it must be stable for at least 30 days prior to Screening.)
10. The patient has any other medical condition or is receiving concomitant medication or therapy that would in the investigator's opinion compromise his or her safety or compliance with the study protocol or compromise data collection.
11. The patient has a history or evidence of drug or alcohol abuse in the 12 months before Screening.
12. The patient has a hypersensitivity, allergy, or contraindication to plecanatide.
13. The patient has received any experimental drug, including linaclotide and lubiprostone, or experimental therapy within 30 days of study start.
14. The patient is unable to tolerate protocol-prescribed rescue medication (Dulcolax®), or unwilling to use it as the only laxative for the duration of the trial.
15. The patient has taken a protocol-prohibited medication prior to randomization.
16. The patient and his or her parent/guardian are unable to communicate well with the study staff and comply with the study requirements (restrictions, appointments, and examination schedule). (The patient must be able to complete all required Daily BM and Symptom electronic diary entries during the Screening/Baseline period and for the duration of the study. The patient must also agree to receive a reminder daily via phone should he or she not complete the daily electronic diary entries.)

Exclusion Criteria Based on Baseline Diary Entries

17. Completion of < 5 of the 7 required daily diary entries in each week of the 2-week baseline diary assessment.
18. Use of rescue medication (Dulcolax®, bisacodyl) for more than 2 days during either of the two weeks of the 2-week baseline diary assessment.
19. ≥ 3 SBM per week for either week of the 2-week baseline diary assessment.

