3.3 PREVIOUS AND CONCOMITANT MEDICATIONS

Any medication the patient takes other than the study drug, including herbal and other non-traditional remedies, is considered a concomitant medication. The following information must

be recorded in the eCRF for each concomitant medication: generic name, route of administration, start date, stop date, dosage, and indication. Any changes in the dose or regimen of a concomitant medication must also be recorded in the eCRF.

At the Screening visit, patients will be asked what medications they have taken during the last 30 days. At each subsequent study visit, patients will be asked what concomitant medications they are currently taking. Use of rescue medication will be recorded daily in the BM Diary and should not be included under concomitant medications.

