3.3.1 Permitted Concomitant Medications

Rescue Medication (RM) – Dulcolax®

Dulcolax® 5 mg tablets will be dispensed to patients at Visit 1, and re-supplied at the study visits as needed. From Visit 1 and for the duration of the trial, only protocol supplied Dulcolax® is to be used as the “rescue medication” (laxative) - no other laxatives are allowed. As per Dulcolax® package insert (directions for use), Dulcolax® “may be taken 1 to 2 tablets as a single dose per day”.

Patients are instructed to take rescue medication only if it has been at least 72 hours since their last bowel movement. A patient is therefore expected to have no more than two days of RM use in any given week.

Rescue medication usage will be recorded daily via the electronic diary. Sites will review rescue medication use with patients during their study visits and have the option to discontinue participation of patients who do not adhere to rescue medication guidelines.

Patients are advised NOT to take rescue medication for the period from 24 hours before to 72 hours after Day 1 of dosing. This avoids confounding the data collected in the first week of study drug administration and allows for accurate determination of the time to first BM.

Dulcolax® will be distributed to sites by Sharp Corporation. Sites may order additional bulk supplies of rescue medication by submitting a Dulcolax® Request Form. Supplies of Dulcolax® will not be reconciled at the completion of the study. Sites must track inventory of rescue medication supplies for the purpose of ensuring adequate quantities for re-supplying patients as needed. The site’s supply of rescue medication will not be managed nor automatically re-supplied.

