- Enter the time of the bowel movement in 12 hour format, entering 2 digits for the hours and 2 digits for the minutes.
- For AM press 1. For PM press 2.
- Did you feel like you completely emptied your bowels during this bowel movement? If yes, press 1, if no press 0.

Please refer to the Bristol Stool Scale diagram provided by your doctor's office. Please rate the form/consistency of this stool. For Type 1, press 1, For Type 2, press 2, For Type 3, press 3, For Type 4, press 4. For Type 5, press 5. For Type 6, press 6. For Type 7, press 7.

Rescue Medication usage

- Have you taken any Dulcolax® today? If yes, press 1, if no press 0.
- How many times have you taken Dulcolax® today?
- Enter the time you took Dulcolax® in 12 hour format, entering 2 digits for the hours and 2 digits for the minutes.
- For AM press 1. For PM press 2.
- Enter the number of tablets you took

Daily Symptom Diary

The patient will be asked to rate their symptoms on a scale of 0 to 10, where 0 is NO 'ABDOMINAL PAIN' and 10 is 'ABDOMINAL PAIN' AS BAD AS YOU CAN IMAGINE.

1. Abdominal Pain. Rate your abdominal pain at its worst on a scale of 0 to 10, where 0 is NO PAIN and 10 is PAIN AS BAD AS YOU CAN IMAGINE.
2. Abdominal Bloating. Rate your abdominal bloating at its worst on a scale of 0 to 10, where 0 is NO ABDOMINAL BLOATING and 10 is ABDOMINAL BLOATING AS BAD AS YOU CAN IMAGINE.
3. Abdominal Discomfort. Rate your abdominal discomfort at its worst on a scale of 0 to 10, where 0 is NO ABDOMINAL DISCOMFORT and 10 is ABDOMINAL PAIN AS BAD AS YOU CAN IMAGINE.
4. If you had one or more bowel movement today, rate your straining with a bowel movement at its worst on a scale of 0 to 10, where 0 is NO STRAINING WITH A BOWEL MOVEMENT and 10 is STRAIN WITH A BOWEL MOVEMENT AS BAD AS YOU CAN IMAGINE.
5. If you had one or more bowel movement today, rate your pain with defecation at its worst on a scale of 0 to 10, where 0 is NO PAIN WITH DEFECATION / WITH A BOWEL MOVEMENT and 10 is PAIN WITH DEFECATION / WITH A BOWEL MOVEMENT AS BAD AS YOU CAN IMAGINE

E. PATIENT QUESTIONNAIRES

Patient Assessment of Constipation -Quality of Life (PAC-QOL), Patient Assessment of Constipation -Symptoms (PAC-SYM), Patient Global Assessment (PGA) Questionnaires

PGA will be administered electronically via IWRS, while PAC-QOL and PAC-SYM are paper-based.

PAC-QOL © PATIENT ASSESSMENT OF CONSTIPATION						

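### Diary rescue entries from the day before the baseline window are not kept, so the 24-hour laxative look-back is cut short on the first baseline day (minor; nearly free to fix)

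*Combined protocol and SAP*

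**What the plan says.** Days are numbered here so that the 14-day baseline window runs from Day -14 to Day -1; Day -15 is the last day before it.

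- **Definition of Terms.** An SBM is "A bowel movement that occurs in the absence of laxative use within the preceding 24 hours".
- **Section 4.2.1, rescue medication.** The diary decides the status: "Use of rescue medication will determine whether a BM was spontaneous".
- **Section 4.2.1, diary activation.** The diary runs from Visit 1, but anything "entered prior to the beginning of the 2-week baseline diary assessment will be utilized for assessment of compliance only and will not be saved".
- **Section 3.3.1.** Dulcolax is dispensed at Visit 1, so it can be used during diary practice. On frequency: "A patient is therefore expected to have no more than two days of RM use in any given week".
- **Section 3.3.** There is no parallel entry in the concomitant medication record: "Use of rescue medication will be recorded daily in the BM Diary and should not be included under concomitant medications".
- **Appendix D.** The rescue item covers the current day only ("Have you taken any Dulcolax® today") and then asks for the time ("Enter the time you took Dulcolax® in 12 hour format").
- **Section 8.4.3.** Baseline SBM and CSBM rates are weekly averages over the last 14 diary days before Day 1. Baseline stool consistency is half the sum of the two weekly average scores.
- **Section 3.2, criterion 19, and Section 5.2.2.** A patient with 3 or more "SBM per week for either week of the 2-week baseline diary assessment" is excluded. The IWRS makes this check; site staff do not evaluate the diary data.

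**The concern.** The SBM definition looks back 24 hours. On 13 of the 14 baseline days, those hours lie within saved diary data. On Day -14 part of them lies on Day -15, whose entries may be used only for compliance and are then not kept. Suppose a patient takes Dulcolax on the evening of Day -15 and has the resulting movement on the morning of Day -14. No usable record then shows that the movement followed a laxative.

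Three things depend on that classification:

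- **Eligibility**, through the programmed check on baseline week 1.
- **Baseline SBM and CSBM rates.** These feed change from baseline, serve as model covariates (Sections 8.8.1.1 and 8.8.2), and enter the 3 + 1 responder definitions (Section 8.8.4.1).
- **Baseline stool consistency**, which Section 8.4.1 scores on SBMs only.

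The patients exposed are those who need rescue just before the window opens. Once entries are gone, no rule written later in the SAP can recover them.

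**Working it through.** **1. Is there another dated record of Day -15 rescue?** None is described. Rescue is kept out of concomitant medications (3.3), and the diary item on Day -14 asks about that day only (Appendix D). Sites review rescue use at visits, but Dulcolax supplies are not reconciled (3.3.1). Section 5.2.2 asks sites to confirm that only study-supplied rescue was used, which gives no dates. The advice in 3.3.1 against rescue from 24 hours before Day 1 concerns the start of dosing; nothing comparable is stated for the start of baseline.

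**2. How much of the look-back is lost?** For a movement at clock hour h on Day -14, h hours are on saved data and 24 - h are not.

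- At 08:00: 8 hours covered, 16 not.
- At 18:00: 18 hours covered, 6 not.

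Rescue taken earlier on Day -14 is timed and saved, so it is still caught.

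**3. Effect on one patient of one false SBM.**

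- Baseline SBM rate: 1/2 = +0.5 per week, against a maximum of 2 per week in an eligible patient. Measured change falls by 0.5.
- Eligibility: 2 true + 1 false = 3 in week 1, which meets criterion 19.
- Stool consistency: a randomized patient has at most 2 recorded SBMs in week 1. The false one therefore makes up 1/2 to all of that week's average, and 1/4 to 1/2 of baseline when week 2 also has a score. The documents give no direction for this effect.
- CSBM: affected only if the patient rated the movement complete.

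**4. The plan's sample size, as the yardstick (Section 8.2).** Inputs: mean changes 1.2 (SD 2.6) and 3.1 (SD 4.0), two-sided 0.05, 80% power, 51 per group.

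- Normal approximation: n = (2.6² + 4.0²)(1.960 + 0.842)² / 1.9² = 49.5, so 50.
- Unequal-variance t-test (noncentral t): power 0.795 at 50 and 0.803 at 51. The stated 51 is reproduced.
- At the planned 30 per group the same calculation gives 0.571.

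**5. Effect on the trial.** Let f be the share of patients with one false SBM. The documents give no value, so a range is shown. If Day -15 is a typical day, rescue follows the two-days-per-week expectation, and each use yields at most one movement, f is at most 2/7. Mean baseline shift = 0.5f. Added variance = 0.25f(1 - f), added to both SDs squared.

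| f (assumed) | Mean shift, SBM/week | Added variance | Power, n = 30 | Power, n = 51 |
|---|---|---|---|---|
| 0 | 0 | 0 | 0.571 | 0.803 |
| 0.05 | 0.025 | 0.012 | 0.571 | 0.803 |
| 0.10 | 0.050 | 0.0225 | 0.570 | 0.802 |
| 1/7 | 0.071 | 0.031 | 0.570 | 0.802 |
| 2/7 | 0.143 | 0.051 | 0.569 | 0.801 |

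**The case against.** **The data must be held anyway.** Baseline is counted back from a Visit 2 whose date can move, so the first baseline day is unknown when early entries are made. On this view the system must hold them until the eligibility report, and not saving them may mean only that they are not kept as study data. It is true that the sentence is hard to apply literally. But it also restricts those entries to compliance, so even data held until Visit 2 could not be used to classify a Day -14 movement.

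**The default is not stated.** No section says how to treat a movement with an incomplete look-back. Final diary text is deferred to the design specifications and Study Procedure Manual, and analysis detail to a later SAP. This stands. Counting the movement as spontaneous is only the likely result, because Section 8.4.1 sums recorded SBMs. Its requirement for an answered rescue question applies only to the exploratory responder analyses.

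**The size is small and the upper bound generous.** This stands. The 2/7 comes from a ceiling on rescue days. A false SBM also needs the movement to fall on Day -14, within 24 hours of the Day -15 dose, with no rescue on Day -14 within the 24 hours before it. Because rescue requires 72 hours without a movement, a patient at that ceiling would rarely also have two true SBMs in a week. The exclusion example therefore fits a lighter rescue user, and its frequency cannot be estimated. Errors can exclude patients but not admit them wrongly, and re-screening is possible with Medical Monitor approval (5.2.1).

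**A stronger reading on the moving window.** A reader might infer that true baseline days are lost when Visit 2 is early. That requires discarding from a planned start date, and no section sets one. Sections 5.2.1, 5.2.2 and 8.4.3 already count the window back from randomization or Day 1.

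**Conclusion.** The point holds as a minor gap. As written, Section 4.2.1 withholds the Day -15 rescue entries that the SBM definition needs on Day -14. One affected movement changes that patient's baseline by 0.5 SBM per week and can cause a wrongful exclusion.

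At trial level it is small: 1 of 14 baseline days, a mean baseline shift of at most about 0.14 per week, and power of 0.569 instead of 0.571 at 30 per group. These figures rest on the assumed ceiling f = 2/7 and at most one false SBM per patient.

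Three further inferences are not supported:

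- **That the look-back cannot be applied on the first day.** It is truncated; same-day rescue is caught.
- **That 14% to 29% of patients (1/7 to 2/7) carry a false SBM.** That is the assumed chance that Day -15 is a rescue day, so only an upper bound.
- **That the comparison with placebo is biased.** The error precedes randomization, is expected equally in all arms, and baseline is a model covariate. The responder definition in Section 8.8.1 uses no baseline.

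**What to change.** In Section 4.2.1, replace the statement that pre-baseline entries are not saved with one that retains diary entries from Visit 1; at minimum, retain rescue dates and times for the 24 hours before the baseline window. Keep practice data out of the baseline values. Use the retained rescue times only to classify movements on the first baseline day, and say so for both the IWRS eligibility check (5.2.2) and the baseline derivation (8.4.3). The window definition needs no change.

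The cost is a line in the diary specification and one in the derivation rules. Patients already make these entries and the system already uses them for compliance, so there is no added patient burden and no effect on sample size. The change has to be made before entries are discarded.
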